7.1.8 Phone Visit 8: Safety Check (visit 7 + 1 day)

The following procedures will be performed at this visit:

- Study staff phone call to assess IN insulin compliance and AEs/SAEs
- Reinforce SipNose device training
- Reinforce daily diary training
- Review CGM data in Clarity

7.1.9 Phone Visit 9: Safety Check (Day 37 +/- 2 days)

The following procedures will be performed at this visit:

- Study staff phone call to assess IN insulin compliance and AEs/SAEs
- Reinforce SipNose device training
- Reinforce daily diary training
- Review CGM data in Clarity

7.1.10 Visit 10: End of Treatment Period 2 (Day 48 +/- 3 days)

The following procedures will be performed at this visit:

- Safety check and assess AEs/SAEs
- Gold score
- Medication review for any changes since screening
- VS (blood pressure/pulse)
- Height/weight/BMI
- MNSI survey
- Hypo surveys (Clarke, HypoAQ)
- Document BG values before and after cognitive testing
- Cognitive tests (study drug must have been taken prior to testing) (RBANS, Trail-making)
- Smell test (12-item UPSIT test versions A & B)
- Review daily diary
- Download SMBG for safety (if used)
- Evaluate CGM for adequate data collected

- Inventory returned devices
- Review CGM data in Clarity
- Provider to see patient at this visit for visit assessment review
- In the event the study site is recommending no non-essential in person clinic contacts (such as during the COVID-19 pandemic), this visit may be done remotely and study staff will obtain as much of the above procedural information as possible. MSNI, VS, height/weight/BMI may not be able to be obtained. Supplies may need to be returned remotely.
- Study visits 10 and 11 may be combined into 1 visit to conclude the patient's participation in the study, with as many of the data points for both of these visits being obtained at the same visit. Any assessments that are able to be done remotely (such as assessment of AE/SAEs) may be done remotely by phone.

7.1.11 Visit 11: Safety Visit (Day 55 +/- 2 days)

The following procedures will be performed at this visit:

- Safety check and assess AEs/SAEs
- Collect vital signs (blood pressure & pulse)
- Obtain laboratory studies (Na, K, CO₂, creat/GFR, AST/ALT, CBC w/ diff) and HbA1c POC
- Perform a standard 12-lead ECG
- C-SSRS questionnaire
- Provider to see patient at this visit for visit assessment review
- In the event the study site is recommending no non-essential in person clinic contacts, this visit may need to be completed as an "essential" visit for safety to document no harm related to the study interventions. Only the VS, laboratory studies and ECG will require in-person evaluation, and the study staff and provider can then follow up with patient by phone to complete the remaining visit items.
- Study visits 10 and 11 may be combined into 1 visit to conclude the patient's participation in the study, with as many of the data points for both of these visits being obtained at the same visit. Any assessments that are able to be done remotely (such as assessment of AE/SAEs) may be done remotely by phone. In the event there are active or unresolved AE/SAEs at the combined visit 10/11, a separate safety phone call 1 week later will be conducted by the study team to assess these AE/SAEs and address as appropriate per investigator.

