5.2 Drug Administration with SipNose

Each dosing administration will require the following items: a) 2 SipNose Devices (2) 2 nose piece covers; b) device holder; c) study drug vial (10 ml vial of regular Insulin (Humulin-R or Placebo)); d) Insulin syringe; e) alcohol wipe; f) needle clipper and/or sharps container.

[figure not shown]

Figure 5: SipNose Device -Sp1N1C1

During the baseline/randomization visit the subject will administer the study drug in front of study personnel to ensure adherence to study protocol for drug administration. To ensure safety and medication compliance, subjects will be followed-up with a routine phone call 1 day and 5 days after baseline/randomization visit, 1 day and 5 days after Visit 7 (start of treatment period 2) and 1 week after final treatment visit.

Devices will be shipped to the clinical study site. One device with a nose piece cover will be supplied for each dose to be administered in the study. Devices are one-time use only. A kit containing all necessary items will be distributed to each subject and replaced at each study visit or as necessary. This will include several extra devices in case there are issues with any devices. Each device is to be loaded with a 10 unit dose of study drug to be used immediately or up to a maximum of 10 minutes prior to IN administration. The Nose Piece and Secondary Drug Container (temporary) are the only components of the device that will come into contact with the study drug and subject's nasal cavity.

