7.1.5 Visit 5: End of Treatment Period 1 (Day 17 +/- 3 days)

The following procedures will be performed at this visit:

- Safety check and assess AEs/SAEs
- Gold score (for data collection purposes only)
- Medication review for any changes since screening
- VS (blood pressure/pulse)
- MNSI survey
- Hypo surveys
- Document BG values before and after cognitive testing
- Cognitive tests (study drug must have been taken prior to testing)
- Review daily diary
- Evaluate CGM for adequate data collected
- Inventory returned devices
- Download SMBG for safety, if used
- Download and review CGM data
- Provider to see patient at this visit for visit assessment review
- In the event the study site is recommending no non-essential in person clinic contacts (such as during the COVID-19 pandemic), this visit may be done remotely and study staff will obtain as much of the above procedural information as possible. Procedures such as MNSI survey and VS may not be able to be done.

7.1.6 Phone Visit 6: Safety Check 1 Week into the 2 Week Washout (Day 24 +/-2 days)

The following procedures will be performed at this visit:

- Study staff phone call to assess for AEs/SEs

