10.3 Subject Withdrawal

Subject may withdraw from study at any time for any reason without penalty or be terminated from the study by the clinical investigator (see provisions for termination by study team.) Investigational team will document the reason(s) for withdrawal. In the event a subject chooses to withdraw from study before Visit 3, the safety procedures described in Section 7.3 will be performed ideally within 3 days following subject’s decision to withdraw. For all subjects who

withdraw, all final safety assessments will be collected regardless of time elapsed since previous visit. In addition to the termination visit, subjects who withdraw early will be contacted within 7 days by study staff via telephone to assess development of new and/or ongoing AEs and concomitant medications.

Subject's participation may be terminated at the discretion of the investigator. Individuals may be withdrawn for the following reasons:

- Clinically significant adverse events
- Lost to follow-up
- Protocol violations
- Inability to tolerate study medication
- Other

11 Adverse Events (AE) and Serious Adverse Events (SAE)

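### The option to combine Visits 10 and 11 conflicts with the routine one-week call in Section 5.2 and can leave participants with no off-drug AE contact after Period 2

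*Combined protocol and SAP*

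**What the plan says.** Section 5.2 sets out the follow-up calls without any condition: "subjects will be followed-up with a routine phone call 1 day and 5 days after baseline/randomization visit", then "1 day and 5 days after Visit 7 (start of treatment period 2) and 1 week after final treatment visit".

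Sections 7.1.10 and 7.1.11 allow a shorter ending: "Study visits 10 and 11 may be combined into 1 visit to conclude the patient's participation in the study". Neither section gives a reason that must apply or a day for the combined visit. The allowance for clinic restrictions is a separate bullet. Section 7.1.11 adds a condition: "In the event there are active or unresolved AE/SAEs at the combined visit 10/11, a separate safety phone call 1 week later". On the purpose of that call, the same sentence says that it "will be conducted by the study team to assess these AE/SAEs and address as appropriate per investigator". The call therefore depends on an event already being open, and its stated purpose is to assess that event.

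Section 11.5 records AEs and SAEs until the person withdraws or completes the study.

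Two other parts of the plan are less restrictive. After Period 1, Section 7.1.6 has an unconditional contact one week into the washout ("Study staff phone call to assess for AEs/SEs"), and Section 7.1.7 has an AE check before Period 2 dosing. Under Section 10.3, participants who withdraw early are "contacted within 7 days by study staff via telephone to assess development of new and/or ongoing AEs".

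**The concern.** This is a safety study, and AEs are a listed safety endpoint (Section 4.2). The DSMB is due to convene once the 10 participants have completed (Section 13.2). A site that follows the combined-visit rule as written can close a participant's record without asking about anything that begins after that visit. Such a completer gets less off-drug AE follow-up than the same person had after Period 1, and less than someone who withdrew.

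The end-of-study ECG, laboratory tests and C-SSRS also belong to Visit 11 (Sections 7.1.11, 7.3.2 and 7.3.3), nominally a week after the last treatment visit. If the visits are merged at the end of Period 2, these values are taken at the end of treatment in some participants and about 7 days later in others. Nothing requires the difference to be recorded.

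**Working it through.** **The plan's own figure.** Section 12.4 states 79.8% power with N = 10, a within-subject SD of 1.4% and a margin of 2%. The standard error is 1.4 × √(2/10) = 0.626 and the noncentrality is 2 / 0.626 = 3.194. With 8 degrees of freedom and one-sided alpha of 0.025, the noncentral t gives 79.84%, so the figure reproduces. Only the 5 participants per sequence matter for this point.

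**Follow-up windows, from the visit days in Section 7.1**

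| Interval | Nominal | With visit windows | Scheduled AE contacts |
|---|---|---|---|
| After Period 1: Day 17 ± 3 to Day 31 ± 2 | 31 − 17 = 14 days | 29 − 20 = 9 to 33 − 14 = 19 days | Two (Visits 6 and 7), all participants |
| After Period 2, separate visits: Day 48 ± 3 to Day 55 ± 2 | 55 − 48 = 7 days | 53 − 51 = 2 to 57 − 45 = 12 days | One (Visit 11), all participants |
| After Period 2, combined at Day 48, no active AE | 0 days | – | None |
| After Period 2, combined at Day 48, active AE | about 7 days | – | One call, about the known event |

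The last two rows assume that the combined visit is held at the end of Period 2. The documents do not say so. Section 7.1.10 requires study drug to be taken before the cognitive tests, so a combined visit that includes those tests is probably on treatment.

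**Worst case for insulin exposures.** Insulin is the Period 2 treatment in one sequence of 5. If every participant has a combined visit and none of those 5 has an active AE, 10 − 5 = 5 insulin exposures have a post-treatment AE contact. If the Section 5.2 call is kept, all 10 do. The same count applies to placebo, because the other 5 participants receive placebo second.

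**What that does to sensitivity.** The documents give no rate for delayed events, so the per-participant risk p is assumed and a range is shown. The chance of seeing at least one event is 1 − (1 − p)^n.

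| Assumed p | n = 10 followed | n = 5 followed |
|---|---|---|
| 5% | 40% | 23% |
| 10% | 65% | 41% |
| 20% | 89% | 67% |

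If no delayed event is seen, the one-sided 95% upper bound on the risk is 1 − 0.05^(1/n). That is 26% for n = 10 and 45% for n = 5.

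**The case against.** A reader might infer that merging hides insulin events and so tilts the comparison towards insulin. The documents do not support this. The option is open to both sequences under 1:1 allocation, so insulin-second and placebo-second participants lose the same follow-up. On-treatment AE contacts match in the two periods (Visits 3, 4 and 5 against 8, 9 and 10), and Section 12.3 keeps the safety outcomes descriptive.

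A reader might also infer that every event after the last insulin dose is missed in the insulin-second group. That goes too far. Anything arising before the combined visit is assessed there, and a participant with an open event keeps a call. The text also lets AE assessment be done by phone, so it need not fall on the same day as the in-person procedures, although no later contact is guaranteed.

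It can fairly be argued that nothing expressly cancels the Section 5.2 call. If Section 5.2 governs, no follow-up is lost. Section 5.2 also fits the unmerged schedule loosely, since the contact a week after Visit 10 is then a clinic visit. Section 5 places the final safety visit up to one week after Visit 10, which sets an upper limit and does not settle the matter. Follow-up is unequal even without merging (14 against 7 nominal days), because the washout fixes the Period 1 interval.

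Two limits on the kind of event also stand. Non-severe hypo- and hyperglycemia are not reported as AEs (Section 11.6), and the smell test is at Visit 10, so merging does not move it.

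These arguments narrow the point but do not remove it. One section promises the call to everyone, another restricts it to open events, and a site has no rule for choosing between them.

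**Conclusion.** The conflict between Section 5.2 and Sections 7.1.10 and 7.1.11 is real and should be corrected. If the combined-visit rule is followed and the visit is held at the end of Period 2, a participant without an active AE has no scheduled off-drug AE contact after Period 2, against two contacts over a nominal 14 days after Period 1.

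The consequence is reduced sensitivity for delayed events and mixed timing of the end-of-study ECG, laboratory and C-SSRS values. No bias between insulin and placebo is shown. The figure of 5 of 10 insulin exposures without post-treatment contact is a worst case: it needs every visit to be combined and no active AE in the insulin-second group, and the documents give no expected frequency of combining. The detection probabilities rest on assumed event risks. The primary endpoint, CGM time below 54 mg/dL, and its power do not depend on any of this.

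**What to change.** Reconcile Sections 5.2, 7.1.10 and 7.1.11. State that every participant whose Visits 10 and 11 are combined receives the one-week AE/SAE phone call, whether or not an event is open, and that the call asks about new as well as ongoing events, as Section 10.3 already does for withdrawals. State in Section 11.5 that AE recording stays open until that call. This does not equalise the 14-day and 7-day windows, but it restores the contact that Section 5.2 describes.

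Record whether the end-of-study ECG, laboratory tests and C-SSRS were obtained at the end-of-treatment visit or about 7 days after it, and label them accordingly in the safety tables.

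The cost is at most about 10 short calls and a wording amendment. No visit or sample is added, and the sample size does not change.

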7.2 Early Withdrawal

If subject withdraws from the study after the screening visit, but before visit 2, no further evaluations are necessary. If subject withdraws from the study after visit 2, all safety assessments will be performed (see section 7.3).

7.3 Safety

For all safety assessments described below, any clinically significant change will be recorded as an AE or SAE (see section 11).

7.3.1 Vital Signs

Vital signs will be recorded at all clinic visits. For within subject consistency, brachial artery pressure will be obtained in the routine fashion. Weight/height/BMI will be recorded at screening and at end of study treatment period 2.

7.3.2 ECG

A standard 12-lead ECG will be performed on subjects at screening and at visit 11 (safety visit).

7.3.3 Laboratory Samples

Laboratory tests will be done at screening and at visit 11 (safety visit).

7.4 Early Withdrawal

If subject withdraws from the study after the screening visit, but before visit 2, no further evaluations are necessary. If subject withdraws from the study after visit 2, all safety assessments will be performed (see section 7.3).

7.5 Safety

For all safety assessments described below, any clinically significant change will be recorded as an AE or SAE (see section 11).

7.5.1 Vital Signs

Vital signs will be recorded at all clinic visits. For within subject consistency, brachial artery pressure will be obtained in the routine fashion. Weight/height/BMI will be recorded at screening and at end of study treatment period 2.

7.5.2 ECG

A standard 12-lead ECG will be performed on subjects at screening and at visit 11 (safety visit).

7.5.3 Laboratory Samples

Laboratory tests will be done at screening and at visit 11 (safety visit).

7.6 Neuropsychological Assessment

7.6.1 Columbia-Suicide Severity Scale (C-SSRS)

The Columbia–Suicide Severity Rating Scale (C-SSRS) was designed to quantify the severity of suicidal ideation and behavior⁴¹. In this study, suicidal ideation and behavior will be prospectively assessed using the C-SSRS. The C-SSRS will be administered by trained raters at specified time points, as indicated in table 1 as well as when clinically indicated. Any subjects demonstrating evidence of suicidality will prompt immediate consultation with the site’s on-call psychiatrist for assistance with decision-making and potential referral to behavioral health services.

7.6.2 Repeatable Battery for the Assessment of Neuropsychological Status (RBANS)

The RBANS is a brief, individually administered neurocognitive battery measuring immediate and delayed memory, attention, language, and visuospatial skills.⁴² The RBANS Update is a “pencil-and-paper” test and requires only a stimulus booklet and record form for administration and scoring. It is specially designed for repeat evaluations and includes alternate forms to control for practice effects related to content. The measure is broadly used for clinical diagnostic purposes and has also been increasingly employed as an endpoint in clinical trial investigations of medications believed to impact neurocognitive status. Three versions (A, B, and C) will be used for this study and randomized to visit for participants.

7.6.3 Trail Making Test (TMT) Parts A & B

The TMT Parts A & B is a brief paper and pencil measure of attention, processing speed, and mental flexibility (or set-shifting). The test has been well validated for use with a wide range of subject populations, is easy to administer, and has been shown to be very sensitive in detecting subtle changes in central nervous system compromise and specifically changes in frontal lobe or “executive” functions. Part A requires subjects to connect a series of numbered dots in order as quickly as possible. Part B requires subjects to connect numbered and lettered dots as quickly as possible by alternating back and forth between the two without making mistakes. Scores include both time to completion and various error types.

8 Investigational Product(s)

8.1 Description of Investigational Product

The study will utilize the following investigational products:

- Regular insulin (Humulin-R), intranasal route
- SipNose Intranasal Device (Sections 2, 5 and Investigator brochure)

8.2 Handling and Storage

The study drug (insulin or saline) will be given to subject after training for administration.

Subjects will be instructed to keep unopened and opened study drug at room temperature according to label recommendations.

The study drugs will be kept at study site per label recommendations and institutional Standard Operational Policy. The unopened regular insulin will be stored in the refrigerator, and the saline stored at room temperature. The refrigerator and storage room used will be connected to the centralized temperature monitoring system, Temp Trak, which monitors

temperatures 24/7 and alerts site staff when out of range. Site staff will review and document temperature in Temp Trak once daily each day department is open. Study staff will be responsible for safeguarding and maintaining the master log.

8.3 Treatment Assignment

Randomization to initial drug treatment will use the permuted block method. Investigators will receive sealed envelopes containing sequence of insulin and saline for each group.

8.4 Packaging and Labeling

All study drug will be labeled according to the following specifications:

- Protocol identifier/IRB approval/account/study number.
- Participant ID # or name.
- “Store at room temperature.”
- “Last day to use” date.”
- “Caution: New Drug--Limited by Federal (or United States) law to investigational use”.
- Study contact # [contact]

8.5 Occupational Safety:

No known significant safety risks exist to site personnel in direct or indirect contact with the study drug.

9 Concomitant Medications and Non-Drug Therapies

9.1 Permitted Medications

Any medication not listed in list of Prohibited Medications (Table 3) will be permitted during this study. A record will be kept by site staff detailing doses and indication of any concomitant medications used by subjects.

9.2 Prohibited Medications

Subjects taking prohibited medications at time of screening will not be allowed to participate in study, unless such treatment is discontinued at least 30 days prior to screening. These medications include opiates, benzodiazepines, and barbiturates. Randomized subjects taking a prohibited medication (episodic or PRN) will be considered for study participation on an individual basis.

Table 3: Prohibited Medications

Barbiturates
Benzodiazepines
Opiates
Any non-insulin therapy to treat diabetes mellitus

10 Subject Completion, Compensation and Withdrawal

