5.6 Study Duration

Study participation will last approximately 10 weeks, consisting of a screening visit, 4 study phase visits, 1 follow-up safety assessment visit and at least 5 phone call visits. Subjects will receive treatment with IN insulin for a period of 14-20 days. Subjects who discontinue treatment will continue to complete follow-up measures as possible.

6 Study Population

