6.1 Eligibility Criteria

6.1.1 Inclusion Criteria

- Adult patients (age ≥ 18) with type 1 diabetes diagnosis and a duration of diabetes of at least 10 years
- Gold score < 4
- HbA1c $\geq 6.5\%$ within the last 3 months or at screen visit
- Stable insulin regimen (MDI or insulin pump) for at least 3 months, as deemed stable by principal investigator
- Depression/anxiety medications stable for at least 3 months
- Ability and willingness to wear CGM continuously during study participation
- Participants must use their own smartphone, and have the ability and willingness to use CGM smartphone applications compatible with their smartphone
- Ability and willingness to check SMBG using own supplies, as instructed by study staff
- Ability and willingness to document when having symptoms of hypoglycemia in the CGM smartphone app or in a diary
- If using insulin pump, willing to operate insulin pump without threshold suspend feature or hybrid closed-loop, if applicable
- Proficient in speaking, reading and understanding English in order to complete surveys and testing of cognitive function
- Women of child-bearing age must agree to procure and use contraception throughout the study

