6.1.2 Exclusion Criteria

A subject will not be included for consideration in this study if any of the following criteria are met:

- Pregnancy or planning pregnancy
- eGFR ≤ 30 mL/min per 1.73 m², if available from medical record
- Currently participating in a research study or completed any other research study within 6 months of screening date
- Current or recent use within 3 months of an insulin delivery system that adjusts insulin in response to continuous glucose monitoring (CGM) data (such as an automated insulin delivery system like hybrid closed-loop insulin pump therapy)
- Known dementia or mild cognitive impairment diagnosis
- Diabetic ketoacidosis within the last 6 months
- Use of non-insulin medications to treat diabetes
- Those planning to change diet or exercise regimen during the study
- History of trans-sphenoidal surgery or surgery to the upper part of the nasal cavity, chronic sinusitis, severe deviated septum, or difficulty with smell and/or taste
- Severe psychiatric illness
- Allergy to adhesives, insulin or any components of insulin product
- Subject cannot adequately demonstrate ability to use and deploy the devices as determined by investigator

- Evidence of suicidality using the Columbia-Suicide Severity Rating Scale (C-SSRS)
- Subject has history of any of the following: moderate to severe pulmonary disease, poorly controlled congestive heart failure, significant cardiovascular and/or cerebrovascular events within previous 6 months, condition known to affect absorption, distribution, metabolism, or excretion of drugs such as any hepatic, renal or gastrointestinal disease or any other clinically relevant abnormality or illness that inclusion would pose a safety risk to the subject as determined by investigator.

7 Study Assessments and Procedures

A summary of study events and procedures is outlined in the Study Visit Table (see appendix 5). Demographic and Baseline Assessments

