12.1 Analysis Overview

Discrete variables will be summarized using frequencies and percentages, while continuous variables will be summarized by mean and standard deviation or median and interquartile range, as appropriate. Baseline variables will be compared between groups to ensure randomization achieved a balanced design. Distribution of the outcome variables will be assessed to determine if the planned analyses are appropriate. All analyses will be performed on an intention-to-treat basis. Missing data will be considered to be missing at random and those subjects will be excluded from analysis. If a large proportion of data is missing (>10%), we will compare baseline characteristics between subjects with missing and non-missing data. No adjustment for multiple comparisons will be done. All statistical analyses will be performed in SAS Version 9.4.

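### Section 9.2 leaves the participation of already randomized prohibited-drug users to case-by-case judgement, with assignment known and no protection for the primary analysis

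*Combined protocol and SAP*

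**What the plan says.** Section 9.2 bars anyone on a prohibited drug at screening, "unless such treatment is discontinued at least 30 days prior to screening". On the drugs concerned it says: "These medications include opiates, benzodiazepines, and barbiturates"; Table 3 adds non-insulin diabetes therapy. For those already allocated it then says: "Randomized subjects taking a prohibited medication (episodic or PRN) will be considered for study participation on an individual basis".

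Other sections bear on how that sentence would work in practice:

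- **Eligibility list.** Section 6.1.2 names only the diabetes drugs among the Table 3 classes ("Use of non-insulin medications to treat diabetes").
- **Knowledge of assignment.** The design is placebo controlled, but no blinding is stated for this trial. Under Section 8.3 the investigators hold the sequence envelopes. Under Sections 7.1.2 and 7.1.7 the observed first dose and four-hour stay happen only when the period is an insulin period.
- **Knowledge of results.** CGM data are reviewed at the phone visits (7.1.3, 7.1.4) and at Visit 5 (7.1.5).
- **Power to remove.** Section 10.3 lets the investigator end participation at discretion. Its listed reasons include protocol violations and an open category.
- **Follow-up.** Section 5.6: "Subjects who discontinue treatment will continue to complete follow-up measures as possible".
- **Analysis.** Section 12.1: "All analyses will be performed on an intention-to-treat basis". The same section treats missing data as missing at random and leaves out subjects who have any.

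**The concern.** A decision about who takes part belongs before allocation. Section 9.2 allows it afterwards, by people who know the treatment and may already have seen the data that form the primary endpoint. If the decision leans, even unintentionally, on how a participant is doing on insulin, the comparison loses the protection of randomization. In a trial meant to show no meaningful increase in time below 54 mg/dL, the worrying direction is the loss of participants who did badly on insulin, since that favours a non-inferiority finding.

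**Working it through.** **1. When would use come to light?** The Visit 1 procedures take a medication history. The Visit 2 list includes an eligibility re-check before randomization but no medication review, and most Table 3 classes are absent from Section 6.1.2. The next listed medication review is at Visit 5, the end of period 1, when CGM data are also downloaded and reviewed. Episodic use may therefore first be identified when both treatment and results are in view.

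**2. What happens to a removed subject's data?** Someone whose participation ends before period 2 has no within-subject difference. Under the missing-data rule in Section 12.1 that person is at risk of leaving the primary analysis, despite the intention-to-treat statement.

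**3. Reproducing the plan's power.** Inputs from Sections 12.2 and 12.4: margin 2 points, true difference 0, square root of within mean square error 1.4 points, 5 per sequence, two-sided 95% interval (one-sided 0.025).

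SE = 1.4 × √[0.5 × (1/n₁ + 1/n₂)], df = n₁ + n₂ − 2, and power is the upper tail of the noncentral t beyond the critical value, with noncentrality 2/SE.

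For 5 + 5: SE = 1.4 × √0.2 = 0.626, df 8, critical t 2.306, power 79.84%. This matches the stated 79.8%.

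**4. The same formula after losses, without replacement.**

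| Analysed per sequence | SE | df | Critical t | Power |
|---|---|---|---|---|
| 5 + 5 | 0.626 | 8 | 2.306 | 79.8% |
| 5 + 4 | 0.664 | 7 | 2.365 | 73.4% |
| 4 + 4 | 0.700 | 6 | 2.447 | 66.5% |
| 5 + 3 | 0.723 | 6 | 2.447 | 63.8% |
| 4 + 3 | 0.756 | 5 | 2.571 | 56.8% |

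**5. What selection could do (illustration).** Take the difference as insulin minus placebo, so that non-inferiority needs an upper limit below +2. Hold the within-subject SD at 1.4 and assume that both sequence means are 0.6.

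- All 10 analysed: half-width 2.306 × 0.626 = 1.44; upper limit 0.60 + 1.44 = 2.04. Non-inferiority is not shown.
- Remove one subject with difference *d*. That sequence's mean becomes (5 × 0.6 − d)/4, the estimate is the average of the two sequence means, and the half-width is 2.365 × 0.664 = 1.57.

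| Removed subject's difference (assumed) | New estimate | Upper limit | Non-inferior? |
|---|---|---|---|
| +1 | 0.550 | 2.12 | No |
| +2 | 0.425 | 1.995 | Yes, barely |
| +3 | 0.300 | 1.87 | Yes |

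A +3 difference is not extreme here. The SD of a within-subject difference is 1.4 × √2 = 1.98, so it lies (3 − 0.6)/1.98 = 1.2 SDs above the mean.

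**The case against.** The strongest reply is that the sentence does not order removal. It says that such subjects will be considered, which can mean that they are kept. Eligibility is re-checked before randomization at Visit 2, so the sentence most naturally covers incidental use that arises later. Section 5.6 continues follow-up and Section 12.1 promises intention-to-treat. Discretionary termination exists in Section 10.3 anyway. Ten is the number expected to complete, with up to 20 consented, so losses may be replaceable.

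Much of this is fair. A reader might infer that the protocol removes these subjects, or that Section 9.2 flatly contradicts Sections 5.6 and 12.1. The text supports neither: removal is permitted, not required. But the cover is only partial. Section 5.6 speaks of people who stop treatment, whereas Section 9.2 speaks of study participation. The missing-data rule weakens the intention-to-treat statement. Replacement could restore power but would not undo selection. The overlap with Section 10.3 is a reason to amend both.

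A reader might also infer that the 30-day rule in Section 9.2 conflicts with the 3-month rules in Section 6.1.1. It does not. The former is a washout for prohibited drugs; the latter concern stability ("Depression/anxiety medications stable for at least 3 months" and "Stable insulin regimen (MDI or insulin pump) for at least 3 months"). The criteria are cumulative, so failing any one makes a person ineligible. Someone on a long-standing benzodiazepine for anxiety meets the stability rule, fails Section 9.2, and is simply ineligible. One small ambiguity remains: whether an anxiety drug within the Table 3 classes, stopped more than 30 days but less than 3 months before screening, counts as stable. The absence of three drug classes from Section 6.1.2 is mostly layout, since Section 9.2 already bars them.

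**Conclusion.** The point holds for the post-randomization sentence. Section 9.2 permits decisions on participation that can depend on treatment and results, and this undercuts the stated intention-to-treat analysis. The calculable cost is about 6 points of power for one lost subject (79.8% to 73.4%) and 13 to 16 points for two (to 66.5% or 63.8%). Those figures assume the plan's own inputs, no replacement, and losses unrelated to outcome.

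The size of any selection bias cannot be derived from the documents. They give no frequency of episodic use and no indication of how the discretion would be exercised. The illustration shows only that one decision can reverse a borderline result. The 30-day and 3-month windows form no part of this conclusion.

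**What to change.** 1. Replace the last sentence of the Section 9.2 text. Prohibited-medication eligibility should be settled before the envelope is opened at Visit 2, within the eligibility re-check already listed there. Cross-reference Section 9.2 in Section 6.1.2 so that the re-check covers all Table 3 classes.
2. State that use after randomization is recorded as a protocol deviation, and that CGM collection, follow-up and inclusion in the primary analysis continue whatever is decided about study drug.
3. Align Section 10.3 so that such use is not in itself a reason to end data collection.
4. As a minor clarification, have the sponsor reconcile Sections 9.2 and 6.1.1 on whether a recently stopped anxiety drug in Table 3 counts as stable. Which clinical rule applies is for the sponsor.

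The cost is protocol wording, plus a medication question inside an existing Visit 2 step. The downside is slight noise from the few incidental users who remain in the analysis.
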